9.1 Primary Objective: Phase I

The primary objective of this study is to evaluate the safety and efficacy of TMS as a monotherapy antidepressant in a prospective, randomized, sham-controlled study in adolescents with MDD who have not responded sufficiently to at least one antidepressant medication trial administered at a clinically adequate dose and duration.

9.2 Secondary objectives

Phase I

To evaluate the acute safety of TMS in adolescent subjects.

Phase II

To evaluate the benefit of daily, active, open-label TMS in Phase I subjects who did not receive protocoldefined clinical benefit from their assigned treatment condition in Phase I; either as new acute treatment (sham to active) or as extended treatment course (blinded active to open label active).

Page 24 of 61

Phase III

To evaluate the long term safety of TMS in adolescent subjects.

To evaluate the durability of the acute clinical benefit of TMS treatment over the course of 6 months among subjects who received protocol-defined clinical benefit from their initial acute treatment course(s).

10 Study Design

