Objectives	To evaluate the durability of benefit of TMS treatment over the course of 6 months in subjects who received clinical benefit from acute treatment course(s) (Phase III).
	To evaluate the benefit of daily, active, open-label TMS in Phase I subjects who did not receive protocol-defined clinical benefit; as new acute treatment (sham to active) or as extended treatment course (blinded active to open label active) (Phase II)

	Structural MRI (conducted at specific sites only): To utilize standard morphometric measures to determine structural changes in the brain associated with TMS treatment.
	Phase I: Total of 100 enrolled (50 Active/50 Sham) across sites
Number of Subjects	 Phase II: Subjects from phase I who did not receive protocol-defined clinical benefit from acute treatment will be offered open-label treatment (estimated to be 42 subjects) Phase III: Subject who did meet protocol-defined clinical benefit after acute treatment in Phase I or Phase II will be followed for 6 months post taper (estimated to be 37 subjects) Structural MRI subset: Approximately 25% of subjects of the Phase I population.
Diagnosis and Main Inclusion Criteria	 Male or female outpatients, age 12-21, meeting DSM-5 diagnosis of Major Depressive Disorder, single or recurrent course of illness, of moderate or greater symptom severity CGI-S score ≥ 4 HAMD₂₄, item 1 ≥ 2 and total score at least 20 at screening At the end of the baseline visit, subject must have a HAMD24 score of ≥ 18 and change in score may not be ≥ 25% decrease from that seen at the screening visit Duration of current episode of depression ≥ 4 weeks and ≤ 3 years Resistance to antidepressant treatment in a discrete illness episode defined by the Antidepressant Treatment Record (ATR): Resistance to treatment defined by ATR level 1 through 4 in current episode. If insufficient number of trials in a previous episode Subjects who have been unable to complete an antidepressant trial of adequate dose and duration due to intolerance to antidepressant therapy may be included if they have demonstrated intolerance to ≥ 4 antidepressant medications within one discrete illness episode (current or a previous episode as defined above) For any subject currently receiving antidepressant medication, the clinician must determine that insufficient benefit is being received from this treatment and it is clinically appropriate to discontinue the existing antidepressant.

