Subjects who at the completion of Phase I or II meet blinded criteria for protocol-defined treatment benefit will be followed for 6 months. If symptom worsening occurs (as defined by increase in CGI-S by 1 or more points from Phase III entry score, for 2 consecutive weeks), an acute course of known active TMS will be offered for up to 6 weeks, until symptoms return to the level recorded at entry into Phase III. Clinical assessments will occur biweekly over the phone and monthly at the study site, throughout the duration of the follow up phase. See Appendix C for schedule of events.

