16.5 Adverse Event Reporting Period

For this study, the treatment follow-up period for adverse events is defined as 30 days following the last study visit. Follow up will be documented in the subjects study file.

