#### C. Secondary Study Objectives:

- To evaluate the acute and long-term safety of TMS treatment in adolescent MDD subjects.
- To evaluate the durability of benefit of TMS treatment over the course of 6 months in subjects who received clinical benefit from acute treatment course(s) (Phase III).
- To evaluate the benefit of daily, active, open-label TMS in Phase I subjects who did not receive protocol-defined clinical benefit; as new acute treatment (sham to active) or as extended treatment course (blinded active to open label active) (Phase II)

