## 3. Phase III (Long Term Follow up):

Subjects who achieve protocol-defined clinical benefit from treatment in Phase I or Phase II will be followed for 6 months after treatment.

If a subject experiences re-emergence of depressive symptoms, an acute TMS retreatment course will be initiated. The TMS retreatment course will continue up to 6 weeks until symptom score is at or below Phase III entry score. Each successful retreatment is followed by a 3-week taper. Subjects could receive retreatment on more than one occasion; therefore, any subject could receive up to 72 treatments in Phase III over 6 months, in addition to Phase I and II exposure.

44-02219-204, Rev C 21-JAN-2019

Page 8 of 28

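### The long-term safety objective covers adolescent subjects in general, but six-month safety data are collected only in subjects who benefited, and Phase III safety is not split by active exposure

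*Protocol*

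**What the plan says.** Protocol 9.2 lists under Phase III the objective "To evaluate the long term safety of TMS in adolescent subjects". SAP 1.C has "To evaluate the acute and long-term safety of TMS treatment in adolescent MDD subjects", with no phase label, and the Protocol Study Summary agrees. The durability objective beside it is, by contrast, expressly limited to subjects who benefited.

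Entry to the six-month phase depends on benefit. Protocol 10.1: "Subjects who at the completion of Phase I or II meet blinded criteria for protocol-defined treatment benefit will be followed for 6 months". SAP 3.A.3: "Subjects who achieve protocol-defined clinical benefit from treatment in Phase I or Phase II will be followed for 6 months after treatment". Protocol 13.2 then requires subjects who meet the relapse definition to be withdrawn.

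The fortnightly safety calls, and the Month 6 vital signs, cognition, audiometry and (at some sites) MRI, appear only in the Phase III schedule (Protocol 10.2 and Appendix C). For everyone else Protocol 16.5 applies: "the treatment follow-up period for adverse events is defined as 30 days following the last study visit". Protocol 16.3 adds that reported events are followed until they subside or stabilize. Protocol 11.5 follows withdrawals for an adverse event for 30 days or until resolution.

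SAP 8.B tabulates adverse events by study phase, by term, by severity and by relationship to the device. It names no breakdown of Phase III by earlier active exposure.

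**The concern.** The population named in the objective is wider than the population that supplies the data. Followed subjects are selected on a good outcome at entry and again by withdrawal for relapse. Protocol 8.4 itself says that adolescents with persistent depressive symptoms are more likely to be hospitalized and suicidal. For those two outcomes, six-month rates in benefiters can be expected to look better than rates in all treated subjects. The sentence does not support the same argument for hearing or cognition.

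The followed group is also mixed in exposure. A sham subject who meets the benefit criteria in Phase I goes to Phase III without an active session, and pooling such subjects dilutes any late effect of the device. Splitting by Phase I arm alone misclassifies in the other direction, because a sham subject who benefited in Phase II has had a full active course. Protocol 8.4 states that the long-term effects of TMS are unknown, so the scope of this conclusion matters.

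**Working it through.** **1. The plan's own exposure figure.** Phase I without taper is at most 30 sessions in 6 weeks. Phase II with taper is 30 + 6 = 36 sessions in 9 weeks. Total: 30 + 36 = 66 sessions in 6 + 9 = 15 weeks. This reproduces the figures in the Protocol Study Summary and SAP 3.A.2.

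**2. How long each subject is observed.** Days run from the first treatment, taking the last taper visit as the last study visit and counting six months from the end of taper.
- Phase II non-benefiter: 15 × 7 = 105 days, plus 30 = about day 135.
- Phase III completer arriving through Phase II: 105 + 180 = about day 285.

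**3. Routes into Phase III and maximum active sessions at entry.**

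| Phase I arm | Benefit in | Active sessions at entry |
|---|---|---|
| Active | Phase I | 36 |
| Active | Phase II | 66 |
| Sham | Phase I | 0 |
| Sham | Phase II | 36 |

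A split by Phase I arm puts the last two rows together, although one is unexposed and the other has had a full course.

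**4. Numbers.** The Study Summary gives "Phase I: Total of 100 enrolled (50 Active/50 Sham) across sites", and estimates 42 for Phase II and 37 for Phase III.
- Outside Phase III: 100 − 37 = 63.
- In neither Phase II nor Phase III: at least 100 − 42 − 37 = 21. The documents do not explain this gap; dropout and refusal are possible reasons.
- In Phase II but not Phase III: between 42 − 37 = 5 (all 37 come through Phase II) and 42 (none do). This too can include dropouts and decliners.

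Neither the arm split of the 42 nor the source of the 37 is given. The number of active-exposed non-benefiters without six-month data therefore cannot be derived.

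**5. What 37 subjects can show.** With no events in n subjects, the upper limit is 1 − α^(1/n).
- One-sided 95%: 1 − 0.05^(1/37) = 7.8%.
- Two-sided 95%: 1 − 0.025^(1/37) = 9.5%.

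The chance of seeing at least one event is 1 − (1 − p)^37. At assumed true rates of 1%, 2% and 5% it is 31%, 53% and 85%. All of these figures refer to benefiters, and to fewer than 37 exposed subjects if sham benefiters are among them.

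**The case against.** The limits are partly visible already. Protocol 9.2 places the objective under Phase III, whose entry rule is open. SAP 7.A makes Phase III analysis descriptive, and SAP 5 gives each phase its own disposition diagram with reasons for discontinuation. This lowers the risk of misreading. It does not change the unrestricted wording in the Study Summary and SAP 1.C, and disposition by phase does not show who had active treatment. The all-enrolled safety set in SAP 3.C creates no data after a subject leaves.

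Stopping visits for treatment failures is a legitimate design choice, since later events would be confounded by other treatments. That stands, and it is a reason to narrow the claim rather than the design.

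Four stronger readings are tempting, and the documents do not support them.
- A reader might infer that non-benefiters have no safety follow-up. They have weekly C-SSRS, end-of-phase cognition, audiometry and vital signs, 30 days of event collection, and follow-up of events until they resolve or stabilize.
- A reader might infer that the most heavily exposed subjects are the ones lost. An active-arm subject who first benefits in Phase II also reaches 66 sessions and enters Phase III, where SAP 3.A.3 allows up to 72 more (66 + 72 = 138).
- A reader might subtract 37 from the active-exposed total. With 0 to 42 of the Phase II subjects coming from sham, this gives 50 − 37 = 13 of 50 (26%) up to 92 − 37 = 55 of 92 (60%). That counts everyone outside Phase III, dropouts and decliners included, so it does not measure non-benefiters.
- A reader might conclude that active-exposed subjects outside Phase III should be telephoned at six months. Selecting them by exposure would reveal Phase I assignment, which the Study Summary and Protocol 13.4 keep blinded until all phases end. The scheduled C-SSRS in Phase III is also confined to retreatment, so a call with that scale would have no counterpart in benefiters who were not retreated.

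**Conclusion.** The concern holds as a mismatch of scope. As written, the objective claims long-term safety in adolescents treated with TMS. The design can describe six-month safety in those who had protocol-defined benefit, an expected 37 of 100 subjects, some perhaps never actively treated before entry. A clean Phase III would exclude, with one-sided 95% confidence, only rates above 7.8%, and only in that group. The direction of bias is supported by the protocol's own statement for suicidality and hospitalization, and for nothing else.

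This rests on the protocol's planning estimates of 42 and 37. The event rates in the detection figures are assumptions. The primary efficacy analysis is unaffected.

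**What to change.** 1. In the Protocol Study Summary, Protocol 9.2 and SAP 1.C, restate the long-term part of the objective, and the conclusion to be reported, as six-month safety in subjects who had protocol-defined benefit. The acute safety objective stays as it is.
2. In SAP 8.B, specify that after unblinding Phase III safety is shown by whether the subject received any active acute course (active in Phase I, or Phase II), not only pooled or by Phase I arm. A sham benefiter who is retreated in Phase III should be marked as exposed from that date.
3. In SAP 5, add the number of active-exposed subjects with no six-month follow-up, with reasons, so that non-benefiters are separated from dropouts and decliners.

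The cost is wording and a few tables from data already collected. There are no new visits, and the blind is not touched before its planned end. If the sponsor wants later contact with subjects outside Phase III, it must be made regardless of Phase I arm.

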10.1 General Design

Screening

Subjects will undergo medical, psychological and neuropsychological assessments to assure compliance with all inclusion and exclusion criteria. Eligible subjects will enter Phase I, randomized acute treatment. See Appendix A for schedule of events.

TMS Treatment

All treatments and motor threshold determinations will be completed by physicians or other health care providers who have been trained to the process based on the NeuroStar User Manual and certified by the Neuronetics study staff. All processes are consistent with the clinical use of the NeuroStar TMS Therapy[®] System.

Motor Threshold (MT) Determination: MT Location and MT Level

The motor threshold location will be determined by visual confirmation of the location on the motor cortex that controls the abductor pollicis brevis (APB) muscle of the thumb. The resting MT level is the minimum power to produce a stimulation response 50% of the time.

Phase I (Randomized, Triple-Blinded): Active Treatment

Stimulation will occur over the left dorsolateral prefrontal cortex at 120% magnetic field intensity relative to the subject's resting motor threshold, at 10 pulses per second for 4 seconds, with an off time, or intertrain interval, of 26 seconds. Repositioning of the coil, per the NeuroStar User Manual, and prophylactic use of acetaminophen or ibuprofen will be allowed for subjects reporting sensations at or near the stimulation site which are uncomfortable or painful. During the first week of treatment only, in the event that the subject cannot tolerate the treatment at these dose parameters, dose intensity may be titrated downward to 110% of the motor threshold, with all other dose parameters remaining the same. Treatment sessions will last for 37.5 minutes (75 trains) to provide a total of 3,000 pulses per treatment session. A total of 30 treatments will be completed within 6 weeks of treatment initiation.

Phase I (Randomized, Triple-Blinded): Sham Treatment

Subjects randomized to sham treatments will have identical schedules, systematic assessments, and treatment approaches to their active treatment counterparts. Neither the adolescents nor the investigators (clinical raters or treaters) will know whether the treatment is active or sham in nature. The sham coil is identical in its appearance to the active coil. Furthermore, Neuronetics, Inc. has created an acoustic matching profile that renders the "sound" of the treatments virtually indistinguishable to subjects or researchers. The acoustic signal creates a painless percussive sensation that will be felt by the subject and will assist in simulating the active condition.

Structural Head MRI Subset (Limited study sites)

Structural MRI comparisons will be acquired for subjects. A consistent MRI technician at each study site will be requested for each of the study scans. Each subject will have a baseline scan and additional scans at the completion of each treatment phase (Phase I and Phase II, if applicable) and at six months post treatment (end of Phase III) or at study discontinuation whichever comes first. The maximum number of scans during the study will be four.

Phase II (Non-Randomized, Open-label):

Subjects who do not meet Investigator site blinded criteria for protocol-defined treatment benefit following Phase I treatment will be offered the opportunity for 30 treatments using the known-active coil. The treatment parameters and methods of assessment in Phase II will be identical to those in Phase I. The only difference will be that the coil used for Phase II will be active and known to the subject and investigators. See Appendix B for schedule of events. The blind will not be broken from Phase I at entry into Phase II.

Taper Phase:

At completion of acute treatment (Phase I or II) and following each retreatment in Phase III, each subject will undergo tapering of the TMS treatment course over three weeks. During week 1, the subject will have 3 treatments (e.g. Mon, Wed, Fri). During week 2, the subject will have 2 treatments (e.g. Mon, Fri) and during week 3, the subject will have 1 treatment (e.g. Fri).

Phase III (Non-Randomized, Open –Label Follow up):

Subjects who at the completion of Phase I or II meet blinded criteria for protocol-defined treatment benefit will be followed for 6 months. If symptom worsening occurs (as defined by increase in CGI-S by 1 or more points from Phase III entry score, for 2 consecutive weeks), an acute course of known active TMS will be offered for up to 6 weeks, until symptoms return to the level recorded at entry into Phase III. Clinical assessments will occur biweekly over the phone and monthly at the study site, throughout the duration of the follow up phase. See Appendix C for schedule of events.

10.2 Efficacy and Safety Assessments

Phase I

See Appendix A for schedule of events.

Outcome Assessments

Trained physicians and raters will administer all diagnostic assessments and clinical interviews determining study eligibility during screening and prior to randomization. All study staff will be trained on study procedures by Neuronetics staff.

Outcome screening will occur after both the Informed Assent/Consent Document and the HIPAA Authorization are signed. Baseline assessments will occur prior to the first TMS treatment session. Outcome measures in Phase I will be assessed at the end of treatment weeks 4 and 6. The following outcome assessments will be completed: HAMD/MADRS structured interview, CDRS-R, CGI-S, and QIDS-A17-SR.

Safety Assessments

A physical and complete medical and psychiatric history will be obtained at the screening visit.

Page 26 of 61

Vital signs including height, weight, blood pressure and heart rate will be collected at the baseline visit and at week 6.

Laboratory determination will be measured at screening and include: Blood chemistry, hematology, urine drug screen, and urine pregnancy for female subjects.

Subjects will be evaluated clinically for adverse events at each visit. Serious adverse events (SAEs) will be recorded as they occur and reported to Neuronetics by the study site within one business day of notification.

Cognitive function assessments will be conducted at the baseline visit and at week 6. The following tests from the NIH Toolbox Cognition Battery are used for this study:

- Education
- Handedness
- Attention
 - o Flanker Inhibitory Control and Attention Test
- Episodic Memory
 - Picture Sequence Memory Test
 - Auditory Verbal Learning Test (Rey)
- Executive Function
 - Dimensional Change Card Sort Test
 - Flanker Inhibitory Control and Attention Test
- Language
 - Picture Vocabulary Test
 - Oral Reading Recognition Test
- Processing Speed
 - Pattern Comparison Processing Speed Test
- Memory
 - List Sorting Working Memory Test

The C-SSRS will be completed weekly during TMS treatment to assess worsening of illness and suicidality. The YMRS will be completed at baseline and will be repeated based on reported change in symptoms.

Air conduction thresholds will be assessed for both left and right ears at the baseline visit and at week 6.

Phase II

See Appendix B for schedule of events. The schedule of efficacy and safety measures for Phase II will be identical to that of Phase I.

Phase III

See Appendix C for schedule of events.

Outcome measures for Follow up Phase III, including HAMD/MADRS structured interview, QIDS-A17-SR, CDRS-R, and CGI-S, will be assessed per schedule of events.

Page 27 of 61

Subjects will be evaluated clinically for adverse events at each visit and at the bi-weekly phone call. The bi-weekly calls are done as a safety check to assess worsening of illness between monthly visits. The phone call will be documented as a progress note and placed with the subjects' source documentation. SAEs will be recorded as they occur and reported to Neuronetics by the study site within one business day of notification.

The C-SSRS will be completed weekly during TMS retreatment session(s). The YMRS will be completed if the interval assessment of spontaneous adverse events indicates the potential occurrence of symptoms of mania or hypomania. In addition, in all subjects receiving TMS retreatment, air conduction thresholds will be assessed for both left and right ears at baseline and at the end of the retreatment block.

Vital signs (including height, weight, blood pressure and heart rate), cognitive function assessments and air conduction thresholds for both ears will be assessed at the end of six-month follow-up.

10.3 Structural Head MRI (Limited study sites)

Analyzed by standard morphometric measures to determine structural changes in the brain associated with TMS treatment. See Appendix A-C for schedule of events.

11 Subject Selection, Enrollment and Withdrawal

All adolescents and their guardians (if applicable) will be provided a careful assent and consent discussion prior to enrollment. Since this is a sham-controlled trial, all subjects would need to understand that during Phase I of the trial, they will be randomized to either the active treatment condition or the sham treatment condition. They will also be informed about the opportunity to receive open, active TMS treatment (during Phase II) if they did not receive protocol-defined clinical benefit during Phase I.

11.1 Inclusion Criteria

Table 2 – Inclusion Criteria

Inclusion Criteria	Determinant
Primary diagnosis of unipolar major depressive disorder, in a current major depressive episode, without psychotic features	M.I.N.I./M.I.N.I. KID (ages up to <18) or (ages ≥ 18) to confirm DSM-5 criteria
Duration of current episode of depression ≥ 4 weeks and ≤ 3 years (the definition of an episode is demarcated by a period of ≥ 2 months when the subject did not meet full criteria for the DSM-5 definition of major depressive episode	Physician evaluation, M.I.N.I./M.I.N.I. KID
$CGI-S \ge 4$	CGI-S
Age is at least 12 and less than 22 years	Self-report and review of medical record
Resistance to antidepressant treatment in a discrete illness episode as defined by the Antidepressant Treatment Record (ATR):	Physician evaluation and review of medical record
• Resistance to treatment defined by ATR level 1-4 in current episode. If insufficient number of trials in the current episode, then must also have failed ≥ 1 and ≤ 4 trials in a previous episode	

 Subjects who have been unable to complete an antidepressant trial of adequate dose and duration due to intolerance to antidepressant therapy may be included if they have demonstrated intolerance to ≥ 4 antidepressant medications within one discrete illness episode (current or a previous episode as defined above) 	
For any subject currently receiving antidepressant medication, the clinician must determine that insufficient benefit is being received from this treatment and it is clinically appropriate to discontinue the existing antidepressant.	
HAMD24 Item $1 \ge 2$ and total score ≥ 20	HAMD24
Subjects able to commit to protocol schedule	Subject and family agreement
Willing to provide informed assent (adolescent) and informed consent (family) for subject < 18 years old or legal requirements of the state Willing to provide informed consent by subject \geq 18 years old or legal requirements of the state	Consent/assent discussion
Signed HIPAA authorization by subject or parent (for subject < 18 years old)	HIPAA authorization

Interim Inclusion Criteria	Determinant
At the end of the baseline visit, subject must have a HAMD24 score of \geq 18 and change in score may not be \geq 25% decrease from that seen at the screening visit	HAMD24

11.2

